anti-HBc	Hepatitis B core antibody
anti-PEG	anti-polyethylene glycol
AST	Aspartate aminotransferase
AUC	Area under the curve
AUC% _{extrap}	Percentage of AUC _{inf} that is due to extrapolation beyond t _{last}
AUC _{0-t}	Area under the concentration-time curve from predose (time 0) to the time of the last quantifiable concentration
AUC _{inf}	Area under the concentration-time curve from predose (time 0) extrapolated to infinite time (AUC _{0-t} + C _{last} /λ _z)
BMI	Body mass index
BP	Blood pressure
bpm	Beats per minute
CHO	Chinese hamster ovary
CL/F	Total body clearance
C _{max}	Maximum serum concentration
hs-CRP	High sensitivity C-reactive protein
DBP	Diastolic blood pressure
DMP	Data Management Plan
DPP-4	Dipeptidyl peptidase-4
ECG	Electrocardiogram
EMA	European Medicines Agency
FiH	First-in-human
PG	Fasting plasma glucose
FSH	Follicle-stimulating hormone
GCP	Good Clinical Practice
HBsAg	Hepatitis B surface antigen
HCV Ab	Hepatitis C antibody
HDL	High-density lipoprotein
HIV	Human immunodeficiency virus
HMC001	Human immunoglobulin G4 Fc fragment

Abbreviation	Definition
IB	Investigator's Brochure
ICF	Informed consent form
ICH	International Council for Harmonisation
IGF-1	Insulin-like growth factor-1
IP	Investigational product
IND	Investigational New Drug
INR	International normalized ratio
IRB	Institutional Review Board
ISEMFs	Intestinal subepithelial myofibroblasts
KGF	Keratinocyte growth factor
LDL	Low-density lipoprotein
ALD-PEG-ALD	Aldehyde-Polyethylene glycol-Aldehyde
MedDRA	Medical Dictionary for Regulatory Activities
MID	Minimum intolerable dose
MTD	Maximum tolerated dose
MRSD	Maximum recommended starting dose
NAb	Neutralizing antibody
NOAEL	No observed adverse effect level
OTC	Over-the-counter
PD	Pharmacodynamics
PK	Pharmacokinetics
PN	Parenteral nutrition
PT	Preferred Term
QTc	QT interval corrected for heart rate
QTcB	QT interval corrected for heart rate using Bazett's correction
QTcF	QT interval corrected for heart rate using Fridericia's correction
RR	Respiratory rate
SAD	Single ascending dose
SAE	Serious adverse event
SAP	Statistical analysis plan
SBP	Systolic blood pressure
SC	Subcutaneous
SD	Standard deviation
SID	Subject identification
SOC	System Organ Class

Abbreviation	Definition
SOP	Standard operating procedure
SUSAR	Suspected unexpected serious adverse reaction
$t_{1/2}$	Terminal elimination half-life
T_{max}	Time of maximum serum concentration
ULN	Upper limit of normal
VLDL	Very low-density lipoprotein
V_z/F	Apparent volume of distribution
λ_z	Terminal elimination rate constant

1. INTRODUCTION

1.1. Background

Hanmi Pharmaceutical is developing HM15912, a synthetic substance produced by combining a GLP-2 analogue [REDACTED]

[REDACTED] This medicinal product is developed as a new treatment for the short bowel syndrome (SBS).

The SBS is a rare disease caused by broad surgical resection of the small intestine or as a result of an inborn condition. It is characterized by a decrease in the intestinal absorption surface area and subsequent malabsorption of essential macronutrients and micronutrients². There is no definitive treatment for the SBS at present, and patients with a short residual bowel are likely to rely on parenteral nutrition (PN). Long-term PN may cause life-threatening complications such as sepsis, osteopenia, and chronic liver diseases³.

GLP-2 is known to increase the intestinal absorption surface area by promoting the growth of crypt cells within the intestine, and it has been developed as a treatment to reduce SBS patients' dependency on PN. GLP-2 is a major hormone that affects many aspects of intestinal physiology such as growth, barrier function, digestion, absorption, movement, and blood flow⁴. The half-life of GLP-2 within the human body is very short (approximately 7 minutes), so the GLP-2 medication currently on the market, teduglutide (GATTEX®), has been developed to have resistance to the dipeptidyl peptidase-4 (DPP-4) enzyme. Of note, however, that the half-life of teduglutide is 1.3~2.2 hours, which is still short, and it is provided as freeze-dried powder, thereby requiring medical staff to go through complicated preparation process to administer it to patients⁵. Thus, teduglutide cannot be a sufficient treatment option for SBS patients requiring long-term PN.

Unlike teduglutide, HM15912 is a GLP product that prolongs the half-life and enhances stability by decreasing renal excretion resulting from increased molecular weight and with recycling of vascular endothelial cells through FcRn binding. [REDACTED]

[REDACTED] The nonclinical PD study results show that HM15912 induced human GLP-2 receptor-mediated cAMP accumulation dose-dependently in hGLP-2R/CHO-K1 cells and stimulated IGF-1 production in mice's primary intestinal subepithelial myofibroblasts (ISEMFs). The secreted IGF-1 binds with the tyrosine kinase IGF-1 receptor in crypt and this is related to crypt cell proliferation through the paracrine signaling. The PD of HM15912 has been verified from in vivo experiments as well. When HM15912 was subcutaneously dosed multiple times to mice and rats, the growth of their intestine, especially the wet weight of their small intestine, has increased dose-dependently and shown higher intestinotrophic efficacy compared to teduglutide. Furthermore, it has been proved that there is a relationship between the physical improvement of intestinal environment and the functional improvement of intestine since the intestinal growth led by HM15912 in SBS rat models has enhanced nutrient absorption as a result. Based on such PD and PK properties, HM15912 is expected to be a promising option for treating the SBS.

Additional details can be found in the Investigator's Brochure (IB)¹.

1.2. Rationale for the Clinical Study

This first-in-human (FiH) study evaluates the safety, tolerability, PK and PD of HM15912, [REDACTED]
[REDACTED]

This study is conducted to define a tolerable dose range for most subjects and to provide exploratory data on the potential for prolonged intestinal absorption increase in healthy population. The results of this clinical study will provide data on design and dose selection for subsequent studies.

1.3. Risk-benefit Assessment

While HM15912 has not been evaluated in humans, clinical experiences with other GLP-2 analogues and known pharmacologic and preclinical data suggest the following expected side effects:

- Gastrointestinal: Abdominal pain, abdominal discomfort, nausea, vomiting, abdominal inflation, dysorexia, colon polyp, small intestinal tumor, intestinal obstruction, gallbladder/biliary tract disease, pancreatic disease
- Respiratory: Upper airway infection, cough
- Immunological: Hypersensitivity reaction
- General: Injection site reaction, pyrexia
- Investigational: Slight increase of amylase and lipase, slight decrease of ALP, ALT, and AST
- Nervous system: Sleep disorder
- Skin lesion: Skin hemorrhage
- Fluid overload

There will be no direct health benefit for healthy subjects from receipt of the investigational product (IP). The protocol has been designed to minimize the risk to research participants. Subjects will be monitored to detect AEs during the study and followed appropriately to ensure resolution of AEs. Sentinel dosing will be employed within each cohort, and available blinded safety data (together with PK/PD data if possible) will be assessed after each dose level to determine if it is safe to escalate to the next planned dose.

2. STUDY OBJECTIVES

2.1. Primary Objective

- To assess the safety and tolerability of HM15912 after single SC doses

2.2. Secondary Objective

- To assess the PK profile of HM15912 after single SC doses

2.3. Exploratory Objective

- To explore the PD properties of HM15912 after single SC doses

3. OVERALL DESIGN AND PLAN OF THE STUDY

3.1. Overview

This is a double-blind, randomized, placebo-controlled, single ascending dose (SAD) study to assess the safety, tolerability, PK and PD of the SC administration of HM15912 in healthy Korean subjects.

The study will be conducted in approximately 5 sequential dosing cohorts, enrolling 8 subjects per cohort. Subjects will be randomized to HM15912 or placebo in a ratio of 6:2 (6 active, 2 placebo). When necessary, one dosing cohort may be added or removed.

Each cohort will be divided in 2 blocks in this FiH study in order to implement the sentinel dosing approach. Within each cohort, the first block will consist of 2 sentinel subjects; 1 subject will receive HM15912, and 1 subject will receive matched placebo. The second block will consist of 6 subjects randomized to receive HM15912 (n = 5) or matched placebo (n = 1). Individual subjects in the second block will be dosed at least 24 hours after the first block when safety and tolerability are found to be satisfactory by the Principal Investigator.

Following an overnight fast of at least 10 hours, each subject will receive a single dose of either HM15912 or matched placebo-administered SC in the abdomen on the morning (8:00 AM - 10:00 AM) of Day 1. Subjects will continue fasting through approximately 4 hours postdose. Water intake is also limited for approximately 1 hour before dosing and approximately 2 hours after dosing.

The planned maximum dose of HM15912 is 1.5 mg/kg; however, higher doses may be administered if safety is confirmed in previous cohorts. If dose is escalated to 1.5 mg/kg or above, MFDS approval will be obtained. After at least 6 subjects (HM15912, n ≥ 4) in each cohort have completed assessments through at least Day 17, blinded safety data will be reviewed and a dose decision/dose escalation decision for the subsequent cohort will be made by the Principal Investigator and the Sponsor. If there are PK/PD data obtained from the preceding or current cohorts, the PK/PD data will be reviewed as well when necessary. Escalation will only proceed if safety and tolerability data related to the dose of the prior cohort are verified. Determination of whether to proceed to the next cohort will be made by the Principal Investigator and the Sponsor, and changes in the dose and the number of cohorts will be approved by the MFDS and the IRB.

PK data will only be reviewed if available. After review of the PK data from the preceding or current cohorts, changes in time points for PK collection, clinical laboratory assessments, and PD collection may be required and will be approved by the MFDS and the IRB.

If dose escalation is stopped based on available blinded safety data, the current dose level will be considered as the minimum intolerable dose (MID). The dose just below the MID will be regarded as the maximum tolerated dose (MTD). If the dose escalation is stopped due to reaching exposure limit without dose-limiting safety findings, the MTD cannot be determined. Dose de-escalation may occur in the last cohort or additional cohorts to further refine clinically relevant dose levels.

Stopping rules are described in Section 3.4.

The study will be comprised of:

- A Screening visit up to 28 days before dosing

- An inpatient assessment period of approximately 8 days, with admission to the institution on Day-1, dosing on Day 1, and discharge on Day 7 once the planned schedule is completed
- Two Outpatient visits on Day 8 (\pm 4 hours), Day 10 (\pm 1 day), Day 17 (\pm 1 day) and Day 30 (\pm 3 days)
- A final Follow-up visit on Day 44 (\pm 3 days)

The total duration of the clinical study per subject will be up to approximately 72 days, including the Screening period.

Procedures related to the clinical study are detailed in the Schedule of Assessments, the PK Sampling Schedule, the Citrulline Sampling Schedule, and the PD Sampling Schedule ([Table 1-1 and 1-2](#), [Table 2-1 and 2-2](#), [Table 3-1 and 3-2](#), respectively).

Doses will be administered via SC injection to subjects in approximately 5 dose cohorts. Additional cohorts may be enrolled and proceed at a dose higher or lower than the planned maximum dose of 1.5 mg/kg, if deemed appropriate by the Principal Investigator and the Sponsor, but cohorts are planned as follows:

Table 4 Cohorts and Dose Administration

Cohorts	Number of Subjects	Treatment ¹
Cohort 1	N = 6	HM15912 0.05 mg/kg
	N = 2	Placebo
Cohort 2	N = 6	HM15912 0.1 mg/kg
	N = 2	Placebo
Cohort 3	N = 6	HM15912 0.5 mg/kg
	N = 2	Placebo
Cohort 4	N = 6	HM15912 1.0 mg/kg
	N = 2	Placebo
Cohort 5	N = 6	HM15912 1.5 mg/kg
	N = 2	Placebo

¹ After at least 6 subjects (HM15912, n \geq 4) in each cohort have completed assessments through at least Day 17, blinded safety data (PK/PD data from the preceding or current cohorts will also be reviewed when necessary) will be reviewed and a dose decision/dose escalation decision for the subsequent cohort will be made by the Principal Investigator and the Sponsor. If dose escalation is stopped, dose de-escalation may occur in additional cohorts to further refine clinically relevant dose levels. The planned maximum dose of HM15912 is 1.5 mg/kg; however, higher doses may be administered if safety is confirmed in previous cohorts.

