3.4. Dose Escalation and Study Stopping Criteria

Dose escalation will be stopped if 1 of the following conditions applies:

- Death of a subject in 1 cohort, at any time, that is considered to be related to the IP, judged by the Principal Investigator
- One or more of the subjects in 1 cohort have experienced serious AE that is considered to be related to the IP, judged by the Principal Investigator.
- Two or more of the subjects in 1 cohort have experienced severe AE that is considered to be related to the IP, judged by the Principal Investigator.
- Two or more of the subjects in 1 cohort have experienced moderate AEs that persist for more than 7 days and are considered to be related to the IP, judged by the Principal Investigator.
- Two or more of the subjects in 1 cohort develop similar clinically significant laboratory, significant ECG or vital sign abnormalities, or severe AEs in the same organ class,

indicating dose-limiting intolerance. Dose escalation may proceed if after review of the data by the Principal Investigator and discussion with the Sponsor, it is concluded that the events are not drug related.

- It is determined that the limit of safety and/or tolerability has been reached. Decision will be made between the Sponsor and the Principal Investigator.

If any delayed reactions occur in subjects administered HM15912 during this study, the Principal Investigator will immediately stop the administration and take appropriate medical measures. If delayed reactions are suspected to be drug hypersensitivity reactions, appropriate medical measures will be taken in accordance with 7.9. Handling of Hypersensitivity Reactions. If Principal Investigator and Sponsor discuss and agree that administering HM15912 to other subjects is an unacceptable risk, they may stop the study as below.

The Principal Investigator and the Sponsor may stop the clinical study after an appropriate discussion if conditions or events including, but not limited to, the following occur during the study. A sufficient written statement on the reason for stopping the study will be submitted to the IRB.

- If clear risks or unacceptable risks are found in the subjects enrolled in this clinical study
- If the Sponsor decides to postpone or stop development of the IP

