5.2.1. Rationale for Dose Escalation

After at least 6 subjects (HM15912, n ≥ 4) in each cohort have completed assessments through at least Day 17, blinded safety data will be reviewed and a dose decision/dose escalation decision for the subsequent cohort will be made by the Principal Investigator and the Sponsor. If PK/PD data have been obtained, they can be reviewed as well. This is not mandatory, however. The parties will decide about the next dose level taking into consideration the outcome from the blinded safety review, the stopping rules (Section 3.4), and the available PK/PD data.

Depending on the nature, frequency and severity of the safety profile observed in the clinical study, the Principal Investigator and the Sponsor will decide one of the followings. If dose is escalated to 1.5 mg/kg or above or dose is reduced from the planned dose, approval of the MFDS and the IRB will be obtained.

1. Proceed with dose escalation and determine the next higher dose;
2. Stop dose escalation (i.e., no further dosing);
3. Investigate a lower dose level (intermediate between the current and prior ones).

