5.2.2. Definition of the Maximum Tolerated Dose

If dose escalation is stopped based on available safety data, the current dose level will be considered as the MID. The dose just below the MID will be regarded as the MTD. If the dose escalation is stopped due to reaching exposure limit without dose-limiting safety findings, the MTD cannot be determined.

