PK data will only be reviewed if available. After review of the PK data from preceding or current cohorts, changes in time points for PK collection, clinical laboratory assessments, and PD collection may be required and will be approved by the MFDS and the IRB.

If dose escalation is stopped based on available blinded safety data, the current dose level will be considered as the minimum intolerable dose (MID). The dose just below the MID will be regarded as the maximum tolerated dose (MTD). If the dose escalation is stopped due to reaching exposure limit without dose-limiting safety findings, the MTD cannot be determined. Dose de-escalation may occur in the last cohort or additional cohorts to further refine clinically relevant dose levels.

The study will be comprised of:

- A Screening visit up to 28 days before dosing
- An inpatient assessment period of approximately 8 days, with admission to the institution on Day -1, dosing on Day 1 and discharge on Day 7 once the planned schedule is completed
- For Cohort 1~3
  - Two Outpatient visits on Day 10 ( $\pm$  1 day) and Day 17 ( $\pm$  1 day)
  - A final Follow-up visit on Day 30 ( $\pm$  3 days)
- For Cohort 4~5
  - Four Outpatient visits on Day 8 ( $\pm$  4 hours), Day 10 ( $\pm$  1 day), Day 17 ( $\pm$  1 day) and Day 30 ( $\pm$  3 days)
  - A final Follow-up visit on Day 44 ( $\pm$  3 days)

The total duration of the clinical study per subject will be up to approximately 58 days for Cohort1-3 and 72 days for Cohort4-5, including the Screening period.

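### A dose can be labelled intolerable because of events under placebo: the MID/MTD label follows a stop that counts all 8 cohort subjects, and no step checks it against HM15912 recipients

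*Protocol*

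**What the plan says.** Protocol 3.1 ties the label to the stop: "If dose escalation is stopped based on available blinded safety data, the current dose level will be considered as the minimum intolerable dose (MID". SAP 2.1 repeats this and adds: "The dose just below the MID will be regarded as the maximum tolerated dose (MTD". The dedicated definition in Protocol 5.2.2 drops the word blinded but is otherwise the same: "If dose escalation is stopped based on available safety data, the current dose level will be considered as the MID". There is one exception: "If the dose escalation is stopped due to reaching exposure limit without dose-limiting safety findings, the MTD cannot be determined".

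Protocol 3.4 sets the stopping criteria per cohort, without regard to treatment. One subject suffices for a related death or a related serious AE ("One or more of the subjects in 1 cohort have experienced serious AE that is considered to be related to the IP"). Two are needed for related severe AEs, for related moderate AEs lasting more than 7 days, and for similar abnormal findings ("Two or more of the subjects in 1 cohort develop similar clinically significant laboratory", continuing to ECG, vital signs and organ class). The last of these must point to dose-limiting intolerance and can be overridden if the events are judged not drug related. A final criterion is pure judgement: "It is determined that the limit of safety and/or tolerability has been reached".

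Protocol 5.8 and SAP 2.2 let the blind be broken for dose-limiting toxicities or where an escalation decision needs it. The Principal Investigator decides case by case, and individual results are not to be revealed. Table 6 of the protocol classes an AE that cannot be judged as related.

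**The concern.** The label is a statement about HM15912, but the stop that produces it is triggered by a mixed group. Relatedness is normally rated blind, so a placebo subject's event can be rated related and can start or complete a stop. The rule then fixes the MID and MTD, with an exception only for exposure-limit stops. Neither document says that the label is revisited after database lock, when the randomization code is opened. SAP 6.2 tabulates safety by treatment but does not mention MID or MTD.

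Protocol 1.2 gives defining a tolerable dose range as a reason for the study and says that the results will inform dose selection in later studies. A wrong MTD would understate that range by one dose step: 2-fold if the stop is at cohort 2 (0.1/0.05) or cohort 4 (1.0/0.5), 5-fold at cohort 3 (0.5/0.1) and 1.5-fold at cohort 5 (1.5/1.0).

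**Working it through.** The plan gives no operating characteristics for the stopping rule, so there is no figure of its own to reproduce.

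**Inputs.** From the documents: 6 HM15912 and 2 placebo per cohort, five sequential cohorts (Protocol 3.1, Table 4), and thresholds of one or two subjects (Protocol 3.4). Assumed: the probability p that a subject has a qualifying event, for which the documents give no figure.

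**Share of stops, given a stop and no drug effect (allocation only)**
- Lone triggering related SAE on placebo: 2/8 = 25%.
- Triggering pair: C(8,2) = 28 possible pairs. Both on placebo: 1/28 = 3.6%. One of each: 6 × 2 = 12, so 12/28 = 42.9%. Both on HM15912: 15/28 = 53.6%.

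**Same shares if the odds of the event are r times higher on HM15912**
- Lone SAE on placebo: 2/(6r + 2).
- Both of a pair on placebo: 1/(15r² + 12r + 1).
- Mixed pair: 12r/(15r² + 12r + 1).

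| r | Lone SAE on placebo | Pair both on placebo | Mixed pair |
|---|---|---|---|
| 1 | 25% | 3.6% | 42.9% |
| 2 | 14.3% | 1.2% | 28.2% |
| 3 | 10.0% | 0.6% | 20.9% |

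**Unconditional chance that a cohort stops on placebo events alone, same p in both arms**

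Single-SAE rule, per cohort: a = (1−p)⁶ × [1 − (1−p)²]. At p = 0.1%: 0.99401 × 0.001999 = 0.00199, or 0.2%. A wrong MTD needs a lower planned dose, so cohort 1 is left out as a stopping cohort. With q = (1−p)⁸ as the chance of passing a cohort, the total over cohorts 2 to 5 is a × (q + q² + q³ + q⁴). At p = 0.1% this is 0.00199 × 3.921 = 0.0078, or 0.8%.

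| Assumed p | Per cohort | Cohorts 2 to 5 |
|---|---|---|
| 0.1% | 0.2% | 0.8% |
| 0.5% | 1.0% | 3.5% |
| 1% | 1.9% | 6.2% |
| 2% | 3.5% | 9.5% |

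Two-subject rule, exactly the two placebo subjects affected: p² × (1−p)⁶. Here q is the chance of fewer than two events among 8.

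| Assumed p | Per cohort | Cohorts 2 to 5 |
|---|---|---|
| 1% | 0.009% | 0.04% |
| 2% | 0.035% | 0.14% |
| 5% | 0.18% | 0.6% |

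The clear error therefore comes mainly from the single-subject criteria.

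**The case against.** Most of the case on the other side is sound.

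- **Unblinding is available at the right moment.** True, but it is optional. Section 3.4 does not say when to use it, and nothing links an unblinded result to the label.
- **Relatedness and clinical judgement filter placebo events.** A reader might infer that the similar-abnormality criterion fires on a bare count. It does not: the findings must indicate dose-limiting intolerance, and the override applies. The filter lowers the risk but normally works blind.
- **Mixed pairs are not errors.** A reader might add 1/28 and 12/28 and say that 46% of pair stops mislabel the dose. The documents do not support that. In 12 of those 13 pairs an HM15912 recipient had the qualifying event, and a cautious label is defensible.
- **The higher absolute figures need high rates.** A 2% rate of related serious AEs under placebo in screened healthy volunteers is an assumption at the unfavourable end.
- **Little hangs on the label.** MID/MTD is not an objective or endpoint. SAP 6.2 summarizes safety by treatment with pooled placebo, so a careful reader can see whose events caused the stop. The tables expose a wrong label, but they do not correct it.
- **The trial can recover in part.** Protocol 5.2.1 allows the option "Investigate a lower dose level (intermediate between the current and prior ones", and Protocol 3.1 allows de-escalation. Both are optional, and neither withdraws the MID label.

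**Conclusion.** The concern holds in a limited form. The written rule can attach an intolerable-dose label to HM15912 on placebo events alone, and no step would catch it. With no drug effect this is 25% of lone-SAE stops and 3.6% of pair stops. Both shares fall as the drug effect grows, to 10.0% and 0.6% at three times the odds. These figures assume a full 6:2 cohort and a stop with exactly one or two affected subjects. The unconditional rates rest entirely on assumed event rates and are small when those are low. For mixed pairs the fault is that the uncertainty goes unreported, not that the label is wrong.

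A reader might also infer that the stopping rules themselves should count only HM15912 recipients. That does not follow: stopping on blinded counts of the whole cohort is a reasonable precaution for subjects, and only the label needs repair. The change is worth making because it is cheap, but its effect is modest.

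**What to change.** Leave the Section 3.4 stopping rules as they are. State in Protocol 3.1 and 5.2.2 and in SAP 2.1 and 6.2 that an MID/MTD arising from a blinded stop is provisional and is confirmed once, after unblinding, by actual treatment:

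- If none of the triggering events occurred in an HM15912 recipient, report the MTD as not determined, as the plan already does for exposure-limit stops. Add that this does not mean the dose was tolerated.
- If the events are mixed, keep the cautious label. Report the HM15912 and placebo counts behind it and state whether the Section 3.4 criterion is met in HM15912 recipients alone.
- For a stop on the judgement criterion, have the Principal Investigator and the Sponsor record which events led to it, so that the same check can be made.

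Keep the relatedness ratings as recorded, and describe the in-study blinded decision separately.

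The cost is a few sentences and one short derivation, with no new data and no change to how escalation is run. The protocol wording is an amendment and may need IRB approval (Protocol 10.8). The trial may occasionally report no MTD where the current rule would give one.
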